**Table 6-2 Criteria for interruption and re-initiation of Deferasirox treatment**

Dose modifications for deferasirox	
Body weight	
Increase/decrease of weight by >10% compared to Visit 3 (baseline weight) or body weight at last dose adjustment due to change in patient's body weight	Dose of study medication needs to be adapted using Dosing Table (provided in Appendix 14.2 ). Only when weight changes with >10% compared to baseline weight or body weight at last dose adjustment due to change in patient's body weight, dose needs to be adapted. Smaller variations in body weight (<10%) during study, does not require adjustments in dose. In this case, baseline body weight can be used to calculate correct dose.
Investigations (Renal)	
Serum creatinine and/or creatinine clearance	
Single increase in serum creatinine $\geq 33\%$	Maintain dose level and repeat the assessment at next visit as clinically indicated
For pediatric patients: - Single increase $\geq 33\%$ above baseline value (visit 3/week1) and $> \text{ULN}$  For adult patients: - Increases by 33% or more above the baseline (visit 3/week1) measurement, repeat the serum creatinine within 1 week, and if still elevated by 33% or more	Deferasirox dose reduction by 10 mg/kg/day for the DT and by 7 mg/kg/day for the granules is necessary.
	If after a dose reduction, a progressive increase in serum creatinine beyond the ULN is observed, a treatment interruption is mandated. If after dose reduction/interruption, resolution of serum creatinine occurs ( $< 33\%$ ) at the next study visit and within normal limits, dose can be resumed again at 100%. If increase in serum creatinine reoccurs again within 2 months according to guidelines above, therapy needs to be reduced to 50% of the last dose. After 2 months, if the serum creatinine increase does not recur, study medication can be returned to 100% of the last dose.
Creatinine clearance between 40 and less 60 mL/min	Reduce dose with 50%. If after dose reduction, resolution of creatinine clearance occurs ( $> 60 \text{ ml/min}$ ), dose can be resumed again at 100%.
Creatinine clearance $< 40 \text{ mL/min}$ or serum creatinine increases $> 2$ times the age-appropriate ULN	Deferasirox therapy must be discontinued

Dose modifications for deferasirox	
Investigations (Hepatic)	
Isolated direct (conjugated) Bilirubin elevation	
> ULN – 2 x ULN	Maintain dose level

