Gastrointestinal issues (including diarrhea, constipation, nausea, vomiting and abdominal pain)	
Some basic recommendations, based on practical experience, can be made to guide physicians in managing patients who experience diarrhea.
 
At the first sign of diarrhea, consider anti-diarrheal medication such as loperamide. Remind the patient to discontinue any laxative preparations or stool softeners they may be taking and to eat small, frequent meals. Determine if the patient is lactose intolerant. Deferasirox DT contains lactose in the formulation so supplemental lactase may benefit the patient; however the deferasirox granules do not contain lactose. Remind the patient to drink 8 to 10 glasses of clear liquid per day. Suggest that the patient take their deferasirox DT with water, not with orange juice or apple juice until the diarrhea resolves.
 
Should the gastrointestinal issues (including diarrhea, constipation, nausea, vomiting and abdominal pain) persist, study drug may be discontinued if the investigator believes it is in the best interest of the patient. Novartis may be contacted by the investigator to discuss dosing options if the investigator so desires.

All dose modifications should be based on the worst preceding toxicity.	
a Core LFTs consist of ALT, AST, GGT, total bilirubin (fractionated [direct and indirect], if direct (conjugated) bilirubin > 2.0 x ULN), and alkaline phosphatase (fractionated [quantification of isoforms], if alkaline phosphatase > 2.0 x ULN.)	
b "Combined" defined as direct (conjugated) bilirubin increase to the defined threshold concurrently with ALT/AST increase to the defined threshold	
If combined elevations of AST or ALT and direct (conjugated) bilirubin do not meet the defined thresholds, please follow the instructions for isolated elevation of direct (conjugated) bilirubin and isolated elevation of AST/ALT, and take a conservative action based on the degree of the elevations (e.g. discontinue treatment at the situation when omit dose is needed for one parameter and discontinue treatment is required for another parameter). After all elevations resolve to the defined thresholds that allow treatment re-initiation, re-start the treatment either at the same dose or at one dose lower if meeting a criterion for dose reduction	

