#### **7.1.2 Treatment period**

The study treatment duration is 48 weeks. Patient visits will occur weekly for the first 3 weeks of treatment and then every 4 weeks starting from Week 5 until Visit 777 (EOT).

Having completed the screening period, patients who are eligible will be enrolled and randomized to receive either deferasirox DT or deferasirox granules. The target daily dose is calculated by the physician based on the patient's actual body weight.

At the start of treatment, iron chelation naïve patients will receive either deferasirox DT 20 mg/kg once daily or deferasirox granules 14 mg/kg once daily. All ICT pre-treated patients will use a deferasirox DT or an equivalent strength-adjusted granules starting dose corresponding to their pre-washout dose, please refer to [Appendix 14.1](#).

For details on study design and dose adjustments, see [Section 4](#) and [Section 6.2](#).

For details of assessments during the treatment periods, see [Table 7-1](#) and [Table 7-2](#).

After the core phase has ended, the patients who have participated and completed the 48 weeks core treatment phase as per protocol and do not have access to the new formulation will have the possibility to enter the optional extension treatment phase until there is local access to the new formulation (granules or FCT) or up to 5 years, whichever occurs first. If the patient does not enter the optional extension phase they must complete the core EOT visit, 30 day safety follow up and EOS visit.

- Patients who discontinue prior to Visit 17 will complete Visit 777 within 7 days of last dose of study drug. End of study (Visit 778) and safety follow-up will be performed within 30 days last dose was given in the core phase.
- All patients who have completed the core treatment phase per protocol will have an EOT visit (Visit 777) at Week 49. Patients who opt to continue to the optional extension treatment phase will proceed to [Table 7-2](#) to complete the Visit 17 assessments on the same day. At completion of the optional extension treatment phase, or should patients discontinue at any time after starting the extension treatment phase they will complete the End of Treatment of Optional Extension Phase (Visit 779) within 7 days of last dose of study drug. End of study (Visit 780) and safety follow-up will be performed within 30 days last dose was given in the optional extension phase.

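### Table 6-2: the first serum creatinine row overlaps the second, on dose action for children above ULN and, separately, on repeat timing for patients who turn 18

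*Protocol*

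**What the plan says.** The serum creatinine block of Protocol Table 6-2 (Section 6.2.1) opens with two rows.

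- **First row.** The trigger is a single rise in serum creatinine of at least 33%. No age group, ULN condition or baseline visit is stated. The action is: "Maintain dose level and repeat the assessment at next visit as clinically indicated".
- **Second row.** There are two triggers. For paediatric patients it is a single rise of at least 33% over the visit 3 (week 1) baseline that is also above ULN. For adult patients it is a rise of at least 33% over the same baseline, after which the site is to "repeat the serum creatinine within 1 week, and if still elevated by 33% or more". The action for both is: "Deferasirox dose reduction by 10 mg/kg/day for the DT and by 7 mg/kg/day for the granules is necessary".

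A general note under the table says: "All dose modifications should be based on the worst preceding toxicity".

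Three other places bear on this. Section 5.2 limits entry to patients under 18 but lets those who turn 18 stay on, including into the extension. Section 7.1.2 sets weekly visits for the first 3 weeks and 4-weekly visits from week 5. Table 7-2 schedules creatinine monthly in the extension, with extra weekly checks in the first month for patients who switch from DT.

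**The concern.** A dose-modification table should send each laboratory result to one instruction. The first row has no upper bound, so results that meet the second row's triggers also meet the first row's. A site that stops at the first row and a site that reads on can act differently on the same result.

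Renal toxicity is one of three toxicities that the protocol says will be actively monitored, with hepatic toxicity and gastrointestinal hemorrhage (Section 2.1). Amendment 3 set out to give clearer dose-modification guidance for raised serum creatinine, citing patient safety. What is at stake is therefore consistent handling of a renal safety signal across sites.

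**Working it through.** No sample size, power or error-rate figure is involved. The check applies each row as literally written to every type of result, then measures the gap between the two repeat times.

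**Step 1. Apply the rows.** I take adult to mean 18 or over, as Section 7.2.4.6.2 does when it changes the creatinine clearance formula. I take single to mean not yet repeated.

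| Patient and result | First row | Second row | Outcome |
|---|---|---|---|
| Any patient, rise below 33% | not met | not met | no conflict |
| Child, single rise ≥33%, at or below ULN | maintain; repeat next visit | not met | no conflict |
| Child, single rise ≥33%, above ULN | maintain; repeat next visit | reduce; no repeat time given | **dose action conflicts** |
| Adult, first rise ≥33%, any ULN status | maintain; repeat next visit | repeat within 1 week; reduce only if still ≥33% | **repeat time conflicts** |
| Adult, rise ≥33% confirmed on repeat | no longer a single rise | reduce | no conflict |

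The paediatric conflict is a subset relation: results that are ≥33% and above ULN lie wholly inside results that are ≥33%. Both paediatric triggers refer to a single increase, so confirmation does not separate them. For adults confirmation does separate the dose actions, and only the timing of the repeat remains in conflict.

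**Step 2. Size the timing conflict.** Core visits fall at weeks 1, 2, 3, 5, 9 and every 4 weeks to week 49.

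| Interval | Days to next visit | Days beyond 1 week |
|---|---|---|
| Week 1 to 2, week 2 to 3 | 7 | 7 − 7 = 0 |
| Week 3 to 5 | 14 | 14 − 7 = 7 |
| From week 5 on | 28 | 28 − 7 = 21 |

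The two repeat times agree up to week 3, differ by 1 week between weeks 3 and 5, and differ by up to 3 weeks after that. These are scheduled gaps, before the visit windows in Section 7.1.

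**Step 3. Compare with the rest of the table.** The isolated bilirubin and ALT/AST steps are bands with lower and upper limits. The 0.5 mg/mg step of the urine protein/creatinine block contrasts a single rise with two consecutive samples. The first creatinine row has neither kind of boundary.

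**The case against.** The strongest reply is that the rows are graded steps: a rise of at least 33%, then that rise plus a value above ULN or confirmation, then, further down, more than twice the age-appropriate ULN, where therapy must be discontinued. A rise of at least 33% that also exceeds twice ULN falls inside the first row too, yet few readers would think the first row overrides discontinuation. The worst-toxicity note supports this reading, and many sites would probably follow the second row because of it. The words about clinical indication in the first row can also be read as leaving some discretion over timing.

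Much of this stands, and it makes the point one of clarity. It does not remove the overlap. The note ranks toxicities; it does not say that the first row excludes values above ULN, and it is silent on when to repeat a test.

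A reader might also infer that one creatinine value draws opposite dose actions and two repeat times at once. The documents do not support that. The dose conflict needs a child above ULN, and the timing conflict needs an adult, because the 1-week repeat appears only in the adult text. A child whose rise stays within ULN meets the first row alone.

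**Conclusion.** The inconsistency is real and has two parts.

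- **Dose action:** maintain against reduce, only for paediatric single rises of at least 33% that are also above ULN.
- **Repeat time:** next visit against within 1 week, only for patients who turn 18 on study. The difference is up to 21 days from week 5.

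This rests on the literal wording and on the readings of adult and single given above. The documents give no count of patients in either group. Saying that every paediatric result meeting the reduction trigger also meets the maintain trigger only restates the subset relation; it does not measure how often the conflict occurs.

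Two stronger readings should not be drawn. A reader might infer that renal toxicity is the drug's main monitored toxicity, but the protocol lists it with two others and does not rank them. A reader might also infer harm to the ferritin and compliance co-primary endpoints. Section 6.2.1 does link dose-adjustment records to the evaluation of compliance, but nothing shows or sizes an effect, and the same table governs both arms. Amendment 6 records that the primary analysis was completed on 07-Dec-2018, so rewording now cannot alter those endpoints.

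The point is worth correcting because it concerns a renal safety instruction and the correction is cheap.

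**What to change.** The sponsor should reconcile the first two serum creatinine rows of Table 6-2 so that each result falls under one row, with one dose action and one repeat time for each age group. The table should also say how the worst-toxicity note applies within this block. Which dose action and which repeat time apply is for the sponsor to decide; none is proposed here.

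The cost is table wording in a protocol amendment and a notice to sites. If dosing has already ended, the study report should instead state how sites applied the two rows.

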#### 6.1.1 Dosing regimen

Having completed the Screening period (including the 5-day chelation washout period for patients previously treated with iron chelators), eligible patients for the core phase will be randomized to one of the following Treatment Arms in a ratio of 1:1:

- Treatment Arm 1 with deferasirox DT
- Treatment Arm 2 with deferasirox granules

At the start of treatment, ICT naïve patients will receive either deferasirox DT 20 mg/kg once daily or deferasirox granules 14 mg/kg once daily. All ICT pre-treated patients will use a deferasirox DT or an equivalent strength-adjusted granules starting dose corresponding to their closest pre-washout dose, please refer to [Appendix 14.1](#).

When creatinine clearance at study start is  $\geq 40$  ml/min and  $< 60$  ml/min (where locally applicable), starting dose needs to be reduced by 50%. This means for treatment naive patients that they will need to start at 10 mg/kg for DT and 7 mg/kg for granules. For pretreated patients, they will need to start at 50% of the pre-washout dose when creatinine clearance  $\geq 40$  ml/min and  $< 60$  ml/min during at least one screening visit. For patients with an already existing reduced creatinine clearance ( $\geq 40$  ml/min and  $< 60$  ml/min before study start), a dose reduction of 50% is only necessary when this was not already performed.

In the optional extension phase, all patients will be provided with the granules at visit 17. Patients on DT formulation during the core phase will receive the equivalent strength-adjusted granules dose corresponding to the last DT dose in the core phase taking dose adjustment guidelines into account (please refer to [Table 6-2](#) and [Appendix 14.1](#)). Patients in granules during the core phase will continue on the same dose as was given at the end of the core phase taking dose adjustment guidelines into account. Please refer to [Table 6-2](#) as applicable.

For each patient the daily dose is calculated by the physician based on the patient's actual body weight, and then rounded up or down to the nearest whole tablet/stick pack according to the available strengths of deferasirox formulations (125 mg, 250 mg and 500 mg for the DT and 90 mg, 180 mg and 360 mg for the granules, see [Appendix 14.1](#)).

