**Table 14-1 Patients pre-treated with deferasirox**

Previous dose of Deferasirox DT (mg/kg/day)	Equivalent dose to be used	
	Deferasirox DT (mg/kg/day)	Deferasirox granules (mg/kg/day)
5	5	3.5
10	10	7
15	15	10.5
20	20	14
25	25	17.5
30	30	21
35	35	24.5
40	40	28

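### Table 6-2's fixed cut of 10 (DT) or 7 (granules) mg/kg/day for a qualifying creatinine rise leaves a zero or negative dose in patients on 10/7 or less, and is not reconciled with the starting doses or the clearance row

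*Protocol*

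**What the plan says.** The renal block of protocol Table 6-2 works in steps. A single creatinine rise of 33% or more does not by itself change the dose: "Maintain dose level and repeat the assessment at next visit as clinically indicated". In pediatric patients the cut needs a single rise of at least 33% "above baseline value (visit 3/week1) and" also above the ULN. In adults it needs a 33% rise that persists on a repeat within a week. The action is then: "Deferasirox dose reduction by 10 mg/kg/day for the DT and by 7 mg/kg/day for the granules is necessary". The next step is distinct: "If after a dose reduction, a progressive increase in serum creatinine beyond the ULN is observed, a treatment interruption is mandated". After resolution, whether following a reduction or an interruption, "dose can be resumed again at 100" percent. If the rise recurs within 2 months, "therapy needs to be reduced to 50% of the last dose". Separate rows halve the dose when creatinine clearance is 40 to below 60 mL/min, and stop treatment when clearance is below 40 mL/min or creatinine exceeds twice the ULN.

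For ICT-naive patients whose clearance is 40 to <60 mL/min at study start, section 6.1.1 says "they will need to start at 10 mg/kg for DT and 7 mg/kg for granules". Table 6-1 repeats this, and its footnote limits those starting doses to naive patients. Pre-treated patients in that clearance range start at half their pre-washout dose unless it had already been halved. Table 14-1 ("Patients pre-treated with deferasirox") lists DT levels from 5 to 40 in steps of 5, and granule levels from 3.5 to 28 in steps of 3.5. Section 6.2.1 introduces the table by saying that reductions exist so that a patient who cannot tolerate the schedule can stay on treatment.

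**The concern.** A fixed subtraction is only a reduction if the current dose is larger than the amount subtracted. The protocol permits doses where it is not. At 10/7 the instruction to reduce becomes an instruction to stop, although the row reserves stopping for a further rise after a reduction. Below 10/7 the instruction has no meaning.

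A site facing such a patient can withhold the drug, choose some positive dose, or ask the sponsor, and the text does not settle which. The same event can then be handled and recorded differently between sites. Section 2.6 of the primary analysis SAP requires a non-zero actual dose for a reduction, and counts a zero dose between two non-zero records as an interruption. So the table in which the event appears depends on how the site read the row.

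**Working it through.** **The plan's own figure.** The reduced-clearance start is half the standard naive start: 0.5 × 20 = 10 (DT) and 0.5 × 14 = 7 (granules), as section 6.1.1 and Table 6-1 state.

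**Fixed cut against the 50% cut.** Let d be the current dose and c the fixed cut (10 DT, 7 granules). The dose left after the first qualifying rise is d − c. The dose left under a 50% rule is 0.5d. Levels are those of Table 14-1, in mg/kg/day, DT / granules.

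| Current dose | Left after fixed cut | Left after 50% cut | Fixed cut as % of dose |
|---|---|---|---|
| 5 / 3.5 | −5 / −3.5 | 2.5 / 1.75 | 200 |
| 10 / 7 | 0 / 0 | 5 / 3.5 | 100 |
| 15 / 10.5 | 5 / 3.5 | 7.5 / 5.25 | 66.7 |
| 20 / 14 | 10 / 7 | 10 / 7 | 50 |
| 25 / 17.5 | 15 / 10.5 | 12.5 / 8.75 | 40 |
| 30 / 21 | 20 / 14 | 15 / 10.5 | 33.3 |
| 35 / 24.5 | 25 / 17.5 | 17.5 / 12.25 | 28.6 |
| 40 / 28 | 30 / 21 | 20 / 14 | 25 |

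The two rules agree only where c = 0.5d, that is d = 20/14.

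**Pre-treated patients with clearance 40 to <60.** With a pre-washout DT dose of 20 the start is 10 and the cut leaves 0. With 15 the start is 7.5 and the cut leaves −2.5. With 40 the start is 20 and the cut leaves 10.

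**Overlap with the stopping row.** Under the Schwartz formula in the SAP, clearance is proportional to height divided by serum creatinine. With height and the constant unchanged, a 33% rise divides clearance by 1.33. To remain at or above 40 mL/min the baseline must be at least 40 × 1.33 = 53.2. A baseline of 59.9 falls to 59.9 / 1.33 = 45.0. A 50% rise moves the threshold to 40 × 1.5 = 60, so the whole 40 to <60 band drops below 40. For naive patients starting at 10/7, the zero-dose result therefore stands alone mainly for baselines of about 53 to <60 with rises of about 33% to 50%.

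**Two rows met by one sample.** Section 7.2.4.6.2 calculates clearance each time serum creatinine is collected. A qualifying rise with clearance 40 to <60 meets both the fixed-cut row and the halving row. At 10/7 these give 0 against 5/3.5; at 30/21 they give 20/14 against 15/10.5. If a halving already made at study start is taken to satisfy the clearance row, the choice at 10/7 is zero against no further change. The table does not say.

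**First event against recurrence.** If the last dose means the full dose resumed after resolution, the first cut is larger per day whenever c > 0.5d, that is below 20/14. If it means the already reduced dose, the further cut is (d − c)/2, which is below c for d < 3c = 30/21.

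**The case against.** The strongest reply is that other provisions already cover most of these cases. Part of it stands.

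- The stopping row governs many of the naive patients on 10/7, as computed above. This stands and narrows the point.
- A patient taken to zero is not stranded, because the resumption rule applies after a reduction or an interruption alike. This stands. A reader might infer that patients with the least renal reserve have no workable path; the documents do not support that.
- Section 6.2.1 sends adjustments it does not cover to the sponsor by written request. But this adjustment is covered; the stated rule simply fails. Section 14.2 has a similar route for low-weight patients whose dose cannot be made up from the available strengths. That settles undispensable doses, which are not part of this point.
- A table footnote says the most severe preceding toxicity decides. It does not say which of the two creatinine-related rows governs when both are met.
- Different renal triggers may properly carry different actions, and nothing says a recurrence must be cut harder per day. Assuming the first cut lasts one 4-week visit interval and the recurrence cut 56 days, DT withheld at 15 mg/kg/day is 10 × 28 = 280 against 7.5 × 56 = 420 mg/kg. At 10 it is 280 against 5 × 56 = 280. So the ordering is a question of intent, not a contradiction.

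A reader might also infer damage to the co-primary endpoints. The documents do not show it. FAS-1 holds only naive patients, whereas the 5/3.5 and 15/10.5 starting levels belong to pre-treated patients. The cut is dose-equivalent across arms (7 = 0.7 × 10). No count of affected patients is given. The Amendment 6 rationale records that the primary analysis was already complete.

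**Conclusion.** The contradiction is real and follows from the protocol's own figures. The fixed cut leaves 0 at 10/7 and a negative dose at 5/3.5, both permitted levels, in a row that lists interruption as a separate step. It applies to a qualifying rise only, not to any first rise.

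Those affected are naive patients starting at 10/7 with baseline clearance of about 53 to <60 mL/min, and anyone else on 10/7 or less. The latter include low-dose pre-treated patients and patients brought down by the ferritin or proteinuria rows. The 53 mL/min limit assumes unchanged height and the same clearance at the creatinine baseline as at study start. How many patients this concerns cannot be derived from the documents.

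When the clearance row is met as well, the two orders agree only at 20/14 and no precedence is given. The recurrence ordering below 20/14 depends on the meaning of the last dose and needs only confirmation. Neither bias between arms nor an effect on the co-primary endpoints is claimed.

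**What to change.** Reconcile the serum creatinine row of Table 6-2 with section 6.1.1, Table 6-1, Table 14-1 and the clearance row of the same table. The result should define the action at every permitted dose level, including 10/7 and below. It should name the governing row when the creatinine and clearance criteria are both met, and say whether a halving made at study start counts. It should also say which dose the recurrence rule refers to, and confirm whether the ordering below 20/14 is intended. The sponsor's clinical team chooses the rule.

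For patients already treated, the study report should state what was done when the row was triggered at 10/7 or below. The SAP's dose listings with reasons for change should supply this. The cost is a protocol clarification centred on one row and a short paragraph of reporting, with no new visits, tests or patients.
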